3.3.2.2 Safety Pharmacology

The effect of TQ on the QT interval was evaluated in a study of healthy adult patients. In this study, patients received once daily 400 mg (2 times the approved recommended dosage) doses of TQ for 3 days. The results suggest that the mean increase in the QTcF interval for TQ is less than 20 msec.

3.3.2.3 Pharmacokinetics

In majority of the clinical studies, TQ was administered under fed conditions. Following single dose administration of 200 mg TQ (two 100-mg TQ tablets) in 65 healthy adult patients under fed conditions (a high-calorie, high-fat meal [approximately 1000 calories with 19% protein, 31% carbohydrate, and 50% fat]), the maximum concentration (C_{max}), time to maximum concentration (T_{max}), and AUC_{inf} were determined to be 147 ng/mL, 14 hr, and 70 hr* μ g/mL, respectively. Following administration of a single dose of TQ orally under fasted conditions in healthy adult patients, AUC and C_{max} increased dose proportionally over the dose range from 100 mg to 400 mg. When healthy adult patients received once-weekly administrations of 200 mg TQ orally for ten weeks without a loading dose under fasting conditions, the mean plasma accumulation ratio of TQ was approximately 4.4.

The apparent oral clearance of TQ is approximately 4.2 L/hr (Inter-Individual Variability [IIV]: 23.6 %) in healthy adult patients. The mean terminal half-life following administration of TQ is approximately 16.5 days (range: 10.8 days to 27.3 days) in healthy adult patients. Tafenoquine is greater than 99.5% bound to protein in humans. The apparent volume of distribution of TQ in healthy adult patients is 2470 L (IIV: 24.1%).

3.3.2.4 Efficacy

There have been no clinical studies with TQ in the proposed indication (mild to moderate COVID-19 infection).

3.3.2.5 Safety

The safety of TQ was assessed in clinical studies to support the approval of TQ for prophylaxis of malaria and for radical cure of *Plasmodium vivax* at various doses and regimens in 3,184 patients. The recommended TQ regimen was evaluated in 825 patients in 5 controlled clinical studies. The mean duration of exposure to TQ in these five clinical studies was 21 weeks (range 10-29 weeks). Three studies were conducted in healthy semi-immune (to malaria) volunteers in Ghana or Kenya and were placebo-controlled; a mefloquine arm was included in 2 clinical studies as a benchmark. An additional study, an active comparator (mefloquine) controlled study, was conducted in healthy soldiers deployed in East Timor (Timor Leste), and a placebo-controlled study was conducted in healthy volunteers in the United States and United Kingdom.

Tafenoquine has been generally well-tolerated in clinical studies. The most common adverse events (AEs) include nausea, vomiting, abdominal pain, diarrhea, and reversible vortex keratopathy (whorl-like patterns of corneal epithelial deposits that did not interfere with visual acuity). Gastrointestinal (GI) AEs occurred with a greater incidence in patients treated with TQ compared with placebo and appeared to increase with increasing dose. Methemoglobinemia has been commonly reported following dosing of TQ in all studies and is most likely secondary to TQ-induced oxidative stress within red blood cells (RBCs). Elevations in serum creatinine without changes in glomerular filtration rate have also been observed. Hypersensitivity reactions (urticaria) have been reported in two patients. Hemolytic anemia should be anticipated in patients with glucose-6-phosphate dehydrogenase (G6PD) deficiency; therefore, patients must undergo G6PD deficiency testing and only be enrolled into TQ studies if G6PD-normal.

Refer to the Investigator's Brochure and/or prescribing information ([Section 15.1](#)) for additional information.

3.4 Rationale for the Study

Tafenoquine inhibited SARS-CoV-2 replication and the yield of progeny virus in VERO E6 cells with EC_{50/90s} for the latter endpoint of ~ 2.6/5.1 μ M, and 4-fold greater potency than hydroxychloroquine (see [Dow 2020](#) and the Investigator's Brochure for details on methodology used). Time of addition studies (head to head concentrations of 15 μ M tafenoquine and hydroxychloroquine) were suggestive of either a more robust effect and/or a different mode of action for tafenoquine, with TQ inhibiting viral replication when added early in the viral replication cycle ([Dow 2020](#)).

Whole lung, lung unbound, and plasma concentrations were simulated following administration of the approved dose of TQ for malaria prophylaxis (200 mg on Days 1, 2, 3 and 10), using Certara's Simcyp model for tafenoquine (see [Dow 2020](#) and the [Investigator's Brochure](#) for more details on methods, and the modeling assumptions made). Concentration time profiles over 10 and 60 days were plotted versus the in vitro EC₅₀, EC₉₀, and EC_{90u} values, with the latter calculated after adjustment for non-specific protein binding in the in vitro assay system ([Dow 2020](#)). As is evident from [Figure 2](#), lung unbound concentrations exceed the EC_{90u} for more than 60 days following administration of TQ.

Therefore, it is reasonable to hypothesize that the approved dose of TQ for malaria prophylaxis might reduce viral load in patients with COVID-19 disease, and thereby provide clinical benefit.

Figure 2 Predicted Tafenoquine Concentration-time Curves for Plasma, Lung, and Lung Unbound Following Administration of Tafenoquine

[figure not shown]

Figure 2: Predicted tafenoquine concentration-time curves for plasma, lung, and lung unbound following administration of tafenoquine at the approved dose for malaria prophylaxis (200 mg/day for three days followed by 200 mg one week later), in which the pH of lung tissue was assumed to be 6. The EC₅₀, EC₉₀, and EC_{90u} concentrations from the YR assay are indicated as horizontal lines across the figure.

4 STUDY OBJECTIVES

4.1 Primary

The primary objective is to determine if TQ increases the proportion of patients with clinical recovery from COVID-19 symptoms on Day 12 in patients with mild to moderate COVID-19 disease compared with placebo.

Clinical recovery is defined as:

- Temperature $\leq 37.7^{\circ}\text{C}$ [surface by infra-red or oral]
- Respiratory rate $\leq 24/\text{minute}$ on room air
- Shortness of breath is absent ([Section 15.2.1](#))
- Cough is mild or absent on a patient-reported scale of absent, mild, moderate, and severe ([Section 15.2.2](#))

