6 STUDY DESIGN

6.1 Study Description

This study is a phase 2, multiple-dose, double-blind, placebo-controlled, study to assess the safety and efficacy of TQ in patients with mild to moderate COVID-19. Approximately 275 patients with COVID-19 will be enrolled with the goal of reaching 250 patients meeting the criteria for the mITT population at the end of the study (~125 TQ, ~125 placebo).

After signing the informed consent form, patients will have medical history taken and undergo laboratory testing including G6PD, FDA-authorized RT-PCR from nasopharyngeal [NP] swab specimens) to confirm presence or absence of SARS-CoV-2, pregnancy testing, hematology, blood chemistry, vital signs, O₂ saturation, physical exams, and will be assessed for COVID 19 symptoms including presence/severity of cough, presence/severity of shortness of breath, oral or skin temperature, and respiration rate. Patients who are eligible to participate in the study will be randomized in a 1:1 ratio to TQ or placebo within 2 days of the screening visit and will receive treatment on Day 1. Patients not meeting eligibility criteria will be considered a screen failure. Rescreening is permitted if first SARS-CoV-2 RT-PCR is negative, provided the patient has not been symptomatic for five days when the first dose of study medication is administered.

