6.1.3 Randomization

Eligible patients will be randomized at 1:1 ratio to receive TQ or placebo and stratified by site. Randomization will be performed through a centralized, web-based, validated system that automates the assignment of patients to treatment assignment. The randomization scheme will be reviewed and approved by the sponsor or designee. For study medication dispensation, the Investigator or designee will access the randomization system to determine which blinded study medication bottle the patients will be assigned.

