7 SELECTION AND WITHDRAWAL OF PATIENTS

7.1 Inclusion Criteria

To be eligible to participate in this study, all of the following criteria must be met:

- (1) Male or female, aged ≥ 18 years of age
- (2) Laboratory confirmed infection with SARS-CoV-2 virus by an FDA-authorized RT-PCR test
- (3) Able and willing to give written informed consent;
- (4) Willing to keep a study diary from Study Day 1 to Day 12 [± 1 day] and have daily phone or videoconferences with study team personnel
- (5) At least one of the following clinical symptoms of COVID-19 infection within the 4 days prior to and inclusive of the day of screening:
 - (i) Respiratory rate ≥ 24 /min;
 - (ii) New cough or shortness of breath that has presented within the last 4 days; and/or
 - (iii) Fever $\geq 37.7^{\circ}\text{C}$ (oral or skin surface by infrared)
- (6) Must agree not to enroll in another study of an investigational agent prior to completion of Day 28 of the study;
- (7) Able to take ARAKODA or KODATEF according to Prescribing Information
- (8) Have been symptomatic no longer than 5 days when the first dose of study medication is administered
- (9) If female, agree to use an acceptable method of birth control from the time of consent through 56 days after the last dose of study drug

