12.3 Planned Efficacy Analyses

12.3.1 Analysis of the Primary Efficacy Variable

The proportion of patients with clinical recovery at Day 12 will be analyzed using two methods: a 2x2 contingency table and logistic regression. The contingency table will provide unadjusted estimates of the proportions of patients with clinical recovery at Day 12. Copper-Pearson exact 95% confidence intervals around the recovery proportion within each treatment group will be provided. If 95% or more patients on the TQ arm have clinically recovered, then no logistic regression will be performed due to too few events then a Fisher's exact test will be used to compare treatment groups. However, if the rate is less than that then a logistic regression will be utilized. Treatment group will be the primary independent factor in the logistic regression. Additional covariates will be included in the model for every 10 events observed (eg, if at least 20 events then clinical site will be included, at least 30 events dichotomized number of symptoms (1-2 vs 3-4). Selection of additional covariates will be based on their relationship to the primary endpoint and correlation with other covariates. Patients who do not have a Day 12 visit due to hospitalization for COVID-19 symptoms will be considered treatment failures.

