15.2.2 Cough Severity Scale

Rate your cough as one of the following:

- 1 – absent
- 2 – mild (may need a nonprescription medication)
- 3 – moderate (definitely needed a medication to control)
- 4 – severe (interfered with activities of daily living)

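### A patient can already meet the primary recovery definition before the first dose, and nothing named in the plan separates these patients

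*Combined protocol and SAP*

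**What the plan says.** Section 4.1 defines clinical recovery by four items: temperature at or below 37.7 °C, respiratory rate at or below 24/min on room air, no shortness of breath, and "Cough is mild or absent on a patient-reported scale of absent, mild, moderate, and severe". In Appendix B (15.2.2) the mild grade reads "mild (may need a nonprescription medication".

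Entry under Section 7.1, criterion 5, requires "At least one of the following clinical symptoms of COVID-19 infection within the 4 days prior to and inclusive of the day of screening". The options are a respiratory rate of at least 24/min, "New cough or shortness of breath that has presented within the last 4 days", or a temperature of at least 37.7 °C. No grade of cough is specified, and the symptom need not still be present at dosing.

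The baseline data exist. Section 6.1 says that at screening patients "will be assessed for COVID 19 symptoms including presence/severity of cough, presence/severity of shortness of breath, oral or skin temperature, and respiration rate". Table 1 schedules the same four items again on Day 1, in clinic or self-measured at home.

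Patients are "randomized at 1:1 ratio to receive TQ or placebo and stratified by site" (6.1.3). mITT requires one dose and one later assessment (12.2). Section 12.3.1 allows one model term per 10 events, and names clinical site at 20 events and then "at least 30 events dichotomized number of symptoms (1-2 vs 3-4"). Beyond that, "Selection of additional covariates will be based on their relationship to the primary endpoint and correlation with other covariates". Section 12 leaves full detail to an SAP to be finalised before database lock and unblinding.

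**The concern.** The primary objective is to increase recovery from symptoms. For a patient who meets all four items before the first dose, a Day 12 success means that he or she stayed well or returned to that state. For everyone else it means that symptoms resolved. The headline proportion pools the two, and its meaning depends on how many patients of the first kind are enrolled. A new mild cough is an unremarkable way to enter a trial of mild to moderate disease, so the group may not be negligible.

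Baseline recovery status is the baseline value of the endpoint and would normally be the first candidate for adjustment. The plan names a coarser symptom count instead and leaves other covariates to a selection rule. Two things are at stake: a primary result with a clear meaning, and less room to choose covariates after the outcomes are known.

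**Working it through.** **1. Entry against recovery.**

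| Patient at baseline | Entry (7.1, criterion 5) | Recovery (4.1) |
|---|---|---|
| New mild cough only | met | already met |
| Fever within the 4 days, now settled, no other symptom | met | already met |
| Respiratory rate was raised, now settled, no other symptom | met | already met |
| Temperature exactly 37.7 °C, or rate exactly 24/min, no other symptom | met | already met |
| New moderate cough | met | not met |

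No exclusion in Section 7.2 removes the first four rows.

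**2. The named covariate.** Taken as a baseline count of the four items, mild cough alone scores 1 and severe cough plus fever scores 2. Both fall in the 1-2 category. The count uses symptom data but neither cough severity nor current recovery status, so it does not separate the two kinds of patient.

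**3. The plan's power figure (12.6).** Inputs: 85% and 70%, 125 per arm, two-sided 0.05, logistic regression.
- Log odds ratio = ln[(0.85/0.15)/(0.70/0.30)] = 0.887.
- Variance factor = 1/(0.85×0.15) + 1/(0.70×0.30) = 12.61; standard error = √(12.61/125) = 0.318.
- Wald power = Φ(0.887/0.318 − 1.96) = 79.8%. Exact enumeration of the Pearson test gives 81.7%.

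The stated 80% reproduces.

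**4. Natural reading: 85% and 70% are whole-arm rates.** Power does not depend on the share f already recovered at baseline. What changes is the gain required in patients still to recover, (15 − d·f)/(1 − f) points, where d is the treatment difference among those already recovered. Neither f nor d is in the documents; both are assumed.

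| d (points) | f = 5% | 10% | 20% | 30% |
|---|---|---|---|---|
| 0 | 15.8 | 16.7 | 18.8 | 21.4 |
| 5 | 15.5 | 16.1 | 17.5 | 19.3 |
| 10 | 15.3 | 15.6 | 16.3 | 17.1 |
| 15 | 15.0 | 15.0 | 15.0 | 15.0 |

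**5. Hypothetical reading: 85% and 70% apply only to patients not yet recovered.** Each arm's rate becomes (1 − f)·p + f·r, where r is the assumed Day 12 rate among the already recovered. Example with f = 20% and r = 95% in both arms: 0.8×0.85 + 0.2×0.95 = 87% against 0.8×0.70 + 0.2×0.95 = 75%, exact power 68%.

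| r, tafenoquine/placebo | f = 5% | 10% | 20% | 30% |
|---|---|---|---|---|
| 95%/95% | 79% | 75% | 68% | 59% |
| 95%/90% | 80% | 78% | 74% | 70% |
| 90%/80% | 81% | 80% | 78% | 76% |
| 85%/70% | 82% | 82% | 82% | 82% |

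**6. What adjustment buys.** The likelihood-ratio test of treatment was compared with and without baseline status on the same 200,000 simulated trials per setting, using step 5 rates and f = 10/20/30%. Power changed by +0.5/+1.0/+1.6 points (r = 95%/95%), +0.2/+0.7/+1.1 (95%/90%) and −0.1/0.0/0.0 (90%/80%). A separate check with a stratified test gained about 0.3 to 2.4 points. Type I error with the covariate was 0.051 at f = 30%.

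**7. Room in the model.** Expected non-recoveries are 125×(0.15 + 0.30) = 56 at 85%/70%. At f = 30% they are 125×(0.12 + 0.225) = 43 with r = 95% in both arms, and 125×(0.105 + 0.21) = 39 with r = 100%. A third term (30 events) is comfortable on these means. A fourth (40 events) is not assured: in the 43-event case the chance of fewer than 40 is 27%. Site may also use several parameters.

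**The case against.** The strongest reply is that nothing in the inference breaks. Randomisation protects the comparison. Status at Day 12 is a legitimate endpoint, because Section 3.1 places progression in the second or third week, so a patient who is mild at entry can still get worse and carries information. Secondary endpoints look at each symptom separately, and exploratory ones look at time to resolution and maximum severity. The covariate rule in 12.3.1 could itself select baseline recovery status, and the SAP that Section 12 defers to is not among the documents reviewed. All of this stands, and it is why the point concerns interpretation and pre-specification. It does not remove the point: the primary proportion still mixes two outcomes, and a variable that may be selected later is not a pre-specified one.

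A reader might go further and infer from step 5 that the trial is underpowered. The documents do not support that. Section 12.6 assigns 85% and 70% to the two treatment groups and takes the 70% from placebo patients in a study of nonhospitalised COVID-19. It omits only whether patients already meeting the definition are counted. The loss needs a reading the text does not give, plus values of f and r that appear nowhere.

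A reader might also infer that the plan ignores baseline symptoms altogether. It does not: the symptom count uses them and, with about 56 events expected, would probably enter the model. Its weakness is that it does not separate these patients.

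**Conclusion.** The overlap follows directly from Sections 4.1 and 7.1 and needs no outside data. Type I error, between-arm validity and, on the natural reading of 12.6, the stated power are intact. The cost is that the primary proportion combines recovering with staying well. If 85% and 70% are whole-arm rates and the already recovered gain nothing from treatment, the others must gain 16.7 points at f = 10% and 21.4 at f = 30% in place of 15; if both groups gain equally, 15 points is enough. These figures rest on assumed shares. The point merits correction before unblinding because it is cheap, not because the trial is compromised. The overlap at exactly 37.7 °C and 24/min is minor.

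**What to change.** - In 12.3.1 or the SAP, before unblinding, pre-specify baseline recovery status (meets or does not meet the Section 4.1 definition) as a covariate in the primary logistic regression. Use the last pre-dose assessment: Day 1 where it is documented as pre-dose, otherwise screening.
- Put it in place of the 1-2 versus 3-4 symptom count, so that the one-term-per-10-events rule is respected.
- Keep mITT as the primary set. Report the subset not recovered at baseline as supportive only.
- Add a sentence to 12.6 saying whether 85% and 70% include patients who already meet the definition.
- Reconcile the entry and recovery limits at exactly 37.7 °C and 24/min (minor).

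No entry restriction is recommended. The cost is one covariate from data already collected, one supportive table and small wording changes, with no effect on recruitment. One limit remains: where Day 1 values are missing or not clearly pre-dose, screening status stands in for status at dosing. That gap is up to 4 days by Table 1, or 48 hours by Section 9.2.2.

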4.2 Secondary

Secondary objectives include determining if TQ:

- Increases the proportion of patients with absence of detectable SARS-CoV-2 virus by RT-PCR at Day 12
- Increases the proportion of patients with absence of clinical symptoms by individual symptom at Day 12
- Decreases the hospitalization rate due to COVID-19 disease by Day 12
- Decreases the number of medical follow-up visits by Day 12

4.3 Exploratory

The exploratory objectives are to determine the time to maximum severity of COVID-19 symptoms and time to resolution of COVID-19 symptoms, with COVID-19 symptoms of interest being increased respiratory rate, fever, cough, and shortness of breath.

5 STUDY ENDPOINTS

5.1 Efficacy Endpoints

5.1.1 Primary

- Proportion of patients with clinical recovery of COVID-19 symptoms at Day 12 [± 1 day]

5.1.2 Secondary

- Proportion of patients with negative SARS-CoV-2 RT-PCR on Day 12
- Hospitalization rates due to COVID-19 symptoms (excluding admittance only for administrative or observations purposes)
- Number of COVID-19-related medical follow up visits (Doctor's office or ER visit)
- Proportion of patients with COVID-19 symptoms at Day 12 by individual symptom

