12.2 Analysis Populations for Analyses

Three patient populations will be defined:

- The modified Intention-to-Treat (mITT) population will include all patients who took at least one dose of study medication and had at least one post start of treatment assessment. The mITT population is analyzed as randomized, regardless of which treatment a patient received.
- Safety population: Any patient randomized and received any dose of study drug. Safety population is analyzed based on the actual treatment received.
- The PP population includes all mITT patients completing the Day 12 [± 1 day] in clinic visit without any major protocol deviations. Protocol deviation category (minor or major) will be determined prior to the database lock and unblinding.

Efficacy endpoints will be analyzed for the mITT population. Analyses of efficacy endpoints in the PP population will provide supportive evidence. Safety summaries will be based on the Safety population.

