12.3.2 Other Efficacy Analyses

Dichotomous secondary endpoints will be analyzed in the same manner as the primary endpoint. The number of medical follow-up visits tabulated to determine if the endpoint can be considered continuous or ordinal. If the data are continuous the treatment groups will be compared by t-test. If the frequency distribution indicates few numbers of visits (eg 0, 1, 2, and 3 visits) then the analysis will use a chi-squared test to compare treatment groups. The methods for the conduct of the exploratory efficacy analyses will be provided in the SAP. Other *ad hoc* analyses not specified in the SAP may also be performed to further explore the data to aid in the design of future studies.

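### The Day 12 individual-symptom analyses do not pre-specify whether the patient had that same symptom at screening, so they pool persistence with new onset and give up a modest amount of power

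*Combined protocol and SAP*

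**What the plan says.** The secondary objective in Section 4.2 asks whether TQ "Increases the proportion of patients with absence of clinical symptoms by individual symptom at Day 12". The matching endpoint in Section 5.1.2 is "Proportion of patients with COVID-19 symptoms at Day 12 by individual symptom".

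- **Population** (Section 12.2): "Efficacy endpoints will be analyzed for the mITT population". There is no restriction by baseline symptom.
- **Method** (Section 12.3.2): "Dichotomous secondary endpoints will be analyzed in the same manner as the primary endpoint".
- **Covariates** (Section 12.3.1): one further term per 10 events. The examples are clinical site at 20 events and then "at least 30 events dichotomized number of symptoms (1-2 vs 3-4". Beyond these, "Selection of additional covariates will be based on their relationship to the primary endpoint and correlation with other covariates". If at least 95% on TQ have recovered, Fisher's exact test replaces the regression.
- **Entry** (Section 7.1): "At least one of the following clinical symptoms of COVID-19 infection within the 4 days prior to and inclusive of the day of screening". The list is raised respiratory rate, new cough or shortness of breath, and fever.
- **Screening data** (Section 6.1): patients "will be assessed for COVID 19 symptoms including presence/severity of cough, presence/severity of shortness of breath, oral or skin temperature, and respiration rate". Table 1 also schedules these on Day 1.

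Sections 5.2 and 12.4.1 treat symptoms that first appear after screening as a safety outcome. Section 5.1.3 lists time to symptom resolution as exploratory.

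**The concern.** A patient who qualified on fever alone may have no cough at screening. For the cough endpoint, that patient counts as a success by staying cough-free, while a patient who entered coughing must improve to count. A Day 12 difference in cough could therefore come from faster resolution, from fewer new coughs, or from both, and the planned result does not separate them.

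Screening status of the same symptom is plausibly a strong predictor of its Day 12 status, and it is known before treatment. Leaving it out forgoes precision. The planned symptom count is a weak substitute, because a patient with one or two symptoms may or may not have the one under test. Any further covariates are to be chosen for their relationship to the primary endpoint, not to the symptom being analysed.

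**Working it through.** **The plan's own figure.** Section 12.6 gives 125 per group, 85% against 70% recovery, two-sided alpha 0.05 and 80% power. For a Wald test of the log odds ratio:

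- log OR = ln[(0.85 × 0.30)/(0.15 × 0.70)] = 0.887
- SE = √[1/(125 × 0.85 × 0.15) + 1/(125 × 0.70 × 0.30)] = 0.318
- power = Φ(0.887/0.318 − 1.96) = 79.8%

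The pooled two-proportion formula gives 81.4%. The stated 80% reproduces. The documents give no power for the individual symptoms.

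**Assumed inputs, not in the documents.** Let q be the share with the symptom at baseline, from 30% to 90%. Among these, the symptom persists at Day 12 in 30% on placebo and 15% on TQ (the complements of 70% and 85%). Among the rest, new onset is (A) none, (B) 10% in both arms, or (C) 10% on placebo and 5% on TQ.

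**Formulas, n = 125 per arm.**

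- As planned, with no symptom covariate: Day 12 rate in each arm = q × persistence + (1 − q) × onset. Calling these a and b with mean p̄, power = Φ{[|a − b| − 1.96√(2p̄(1 − p̄)/n)] / √[(a(1 − a) + b(1 − b))/n]}.
- Stratified by baseline symptom (Cochran-Mantel-Haenszel): for stratum size m per arm, difference d and mean rate r, z = Σ(m/2)d / √Σ(m/2)r(1 − r), and power = Φ(z − 1.96).

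**One case in full (A, q = 50%).** The rates are 0.15 and 0.075.

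- Planned: (0.075 − 1.96 × 0.03997)/0.03969 = −0.084, so power is 46.6%.
- Stratified: numerator 31.25 × 0.15 = 4.69; variance 31.25 × 0.225 × 0.775 = 5.45; z = 2.008; power 51.9%.

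**All cases, power in %, planned → stratified on all patients.**

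| New onset, placebo / TQ | q = 30% | q = 50% | q = 70% | q = 90% |
|---|---|---|---|---|
| A: 0 / 0 | 29.3 → 34.3 | 46.6 → 51.9 | 62.6 → 66.1 | 76.0 → 76.9 |
| B: 10% / 10% | 17.6 → 18.1 | 36.1 → 37.1 | 56.7 → 57.5 | 74.5 → 74.5 |
| C: 10% / 5% | 49.4 → 51.3 | 60.1 → 62.0 | 69.7 → 70.9 | 77.9 → 78.1 |
| Only patients with the symptom at baseline (any onset) | 34.0 | 51.9 | 66.4 | 77.2 |

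Simulation with 20,000 trials per case agreed within about 1 point.

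**Larger assumed effects (logistic Wald test, 3,000 simulated trials).**

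- q = 50%, persistence 35% against 15%, onset 2%: 64.3% unadjusted, 70.1% adjusted.
- q = 30%, persistence 45% against 15%, onset 5%: 56.5% unadjusted, 61.2% adjusted.

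A repeat with 4,000 trials gave 64.6% → 69.2% and 57.9% → 61.9%. With no treatment effect (q = 50%, persistence 30% and onset 5% in both arms), the rejection rate was 4.9% unadjusted and 4.6% adjusted.

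**Would the symptom count enter?** Expected patients with the symptom at Day 12 = 125(a + b). In A this is 125 × 0.135 = 17 at q = 30% and 125 × 0.225 = 28 at q = 50%. If these are the events, both fall short of 30. Section 12.3.1 does not define an event, so this is conditional.

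**The case against.** The strongest defence is that the endpoint matches its objective. Section 4.2 asks about absence of each symptom at Day 12 in everyone, not resolution among those affected, and an unadjusted randomised comparison answers that without bias. This stands.

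The components also appear elsewhere, with new onset as a safety endpoint and time to resolution as exploratory. That weakens any claim that the trial cannot examine resolution. It does not help a reader take apart the secondary Day 12 result itself.

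Nor are baseline symptoms wholly ignored. The symptom count may enter, further covariates are possible, and Section 12 describes methods only in general terms, leaving detail to the SAP. The fair statement is that same-symptom status is not pre-specified.

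A reader might infer that analysing only patients who had the symptom recovers much more power. In the two larger-effect cases that restricted analysis reaches 74.5% and 80.9%. Both cases assume TQ does nothing to new onset. If TQ halves onset from 10% to 5%, restriction loses power: 60.1% to 51.9% at q = 50%, and 49.4% to 34.0% at q = 30%. The documents give no onset rate or per-symptom effect to rule this out, so patients without the symptom cannot be dismissed as noise.

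**Conclusion.** The point holds as one of efficiency and interpretation, not bias. The Day 12 symptom comparisons pool persistence with new onset, and the plan does not pre-specify the screening variable that would separate them.

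Adjusting or stratifying on the full mITT population gains about 0 to 6 points of power in the cases tried, with no material loss in any. The gain nears zero when almost everyone has the symptom at baseline, or when new onset is common and unaffected by treatment. Every prevalence, persistence and onset rate here is an assumption.

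The documents do not support reading the planned analysis as invalid. The primary endpoint and its sample size are unaffected. This is an inexpensive improvement to secondary analyses.

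**What to change.** - In each individual-symptom model on the full mITT population, pre-specify screening presence (or grade) of the same symptom as the first covariate after treatment, in place of the 1-2 vs 3-4 count. State where site then falls in the 10-events sequence, and define an event.
- Where events are too few for logistic regression, or the 95% rule would trigger Fisher's test, use a test stratified by that screening status.
- Use screening rather than Day 1 values, because no text guarantees that the Day 1 assessment precedes the first dose. Say whether presence means at the screening assessment or at any time in the 4-day entry window.
- Tabulate Day 12 proportions by arm, descriptively, for patients with the symptom at screening (resolution) and without it (new onset). Do not present the first group as a more powerful test.

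The cost is SAP wording and one table per symptom, with no new data, visits or patients. Section 12 allows changes of statistical method before database lock and unblinding to be documented in the SAP without a protocol amendment.
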